12.6	Data Collection, Record Keeping and Storage	26
13	SUBJECT CONFIDENTIALITY.....	27
14	PUBLICATION POLICY.....	27
	REFERENCES.....	29
	Appendix 1: Study Schedule	31
	Appendix 2: Pain Rating Scale	32
	Appendix 3: Fitzpatrick Wrinkle Classification System.....	33
	Appendix 4: Fitzpatrick Skin Type Classification	34
	Appendix 5: Before and After Treatment Instructions	35
	Appendix 6: Before and After Biopsy Instructions	36
	Appendix 7: Subject Questionnaire	37

Protocol Summary

Title	A Single-Center Open-Label Study of 1064 nm [REDACTED] Laser for Nonablative Skin Rejuvenation
Objective	To evaluate the efficacy and safety of the Cutera excel V Laser Genesis/ 1064 nm [REDACTED] laser for skin rejuvenation.
Study Design	A single-center prospective, open-label uncontrolled study.
Enrollment	15 subjects
Primary Endpoint	
• Degree of improvement at 12 weeks post-final treatment as assessed by independent blinded reviewers (Physician's Global Assessment).
Secondary Endpoints	
• [REDACTED][REDACTED][REDACTED][REDACTED][REDACTED][REDACTED]
Subject Population	Female or male subjects, age 35 to 55 years, Fitzpatrick skin types I-IV
Planned Schedule	First subject enrolled: March 15, 2016 Last subject last visit: January 15, 2017

1 PURPOSE

[figure not shown]
The purpose of this investigation is to evaluate the safety and efficacy of the Cutera excel V Laser Genesis procedure utilizing the 1064nm [REDACTED] laser for skin rejuvenation, specifically improvement of overall skin quality including rhytides, lentigines, erythema, telangiectasia and skin texture.

2 BACKGROUND INFORMATION

2.1 Photo-Rejuvenation

Non-invasive treatment options are in high demand by patients wanting to improve their appearance without surgical intervention. As a result, patients now have a variety of options for non-invasive skin rejuvenation, from laser and light-based treatments to devices that utilize ultrasound and radiofrequency, however this was not always the case. Initial skin rejuvenation procedures utilized ablative lasers, such as the carbon dioxide (CO₂) and erbium:yttrium-aluminum-garnet (Er:YAG), and resulted in substantial improvement in skin appearance, texture, rhytides and laxity[1-3]. However, since ablative treatments destroy the epidermal layer of the skin in order to penetrate and heat the deeper dermal layers, ample post-procedure recovery time is required and patients may experience side effects lasting for a few weeks. Furthermore, hypo- or hyperpigmentation, prolonged wound healing and even scarring can occur following ablative procedures [4-6]. Treatment methods with less risk of side effects and post-treatment down time are in high demand. As such, the choices are vast and varied, ranging from fractional non-ablative laser devices to those that use radiofrequency [7-15]. Fractional lasers inflict microscopic zones of thermal damage in the dermal layers of the skin without destruction of the epidermis, thereby reducing recovery time significantly as compared to ablative procedures[16]. Treatment with non-fractional, non-ablative laser devices requires little to no post-procedure recovery time. Nonablative lasers of various wavelengths are effective for skin rejuvenation based on the principle of selective photothermolysis, whereby laser light is absorbed by hemoglobin in blood vessels and melanin in pigment-producing skin cells [17, 18]. Absorption of laser light by these molecular chromophores results in the production of heat, leading to destruction of unwanted blood vessels and pigment cells. Heat production within the dermis by the laser light also results in immediate collagen contraction and heat-induced wound healing that, over time, causes a cascade of cellular events leading to new collagen production and improved skin appearance [8, 10, 19-23].

2.2 Study Device

[REDACTED]		
[REDACTED]	[REDACTED]	[REDACTED]

3 STUDY OBJECTIVES

The objectives of this study are:

- 1) To evaluate safety of the Cutera excel V Laser Genesis procedure utilizing 1064 nm [REDACTED] laser for skin rejuvenation treatment;
- 2) To evaluate efficacy of the Cutera excel V laser for skin rejuvenation, in particular, improvement of rhytides, lentigines, erythema, telangiectasia and skin texture.

4 STUDY DESIGN

This is a single-center prospective, open-label uncontrolled study in 15 male or female subjects, age 35 to 55 years who desire non-ablative laser treatment for facial photo-rejuvenation, specifically improvement of rhytides, lentigines, erythema, telangiectasia and skin texture. Subjects will receive [REDACTED] laser treatments [REDACTED] and complete [REDACTED] follow-up visits; [REDACTED] at 12 weeks post-final treatment.

[REDACTED]

4.1 Study Endpoints

4.1.1 Efficacy endpoints

4.1.1.1 Primary Efficacy Endpoint

- Degree of improvement at 12 weeks post-final treatment as assessed by independent blinded reviewers (Physician's Global Assessment).

4.1.1.2 [REDACTED]

- [REDACTED]
- [REDACTED]
- [REDACTED]
- [REDACTED]
- [REDACTED]
- [REDACTED]
- [REDACTED]
- [REDACTED]

4.1.2 Safety Endpoint

- Incidence and severity of adverse device effects during the study period, including subject pain level during laser treatment.

4.2 Study Duration

Subjects enrolled will be asked to participate for [REDACTED] : one screening visit, [REDACTED] laser treatment visits, [REDACTED] | [REDACTED] follow-up visits; [REDACTED] 12 weeks post-final treatment.

The screening and first laser treatment may be combined into one visit provided that the informed consent process has been completed (see Section 12.2) and the subject has signed the IRB-approved Informed Consent Form prior to the commencement of any study-related procedures and device treatments.

4.3 Study Effectiveness Assessments

4.3.1 Blinded Assessments

4.3.1.1 Blinded Reviewer's Global Assessment of Improvement

Independent, blinded physician reviewers will be asked to perform an assessment of subject photographs at baseline, [REDACTED] and 12 weeks post-final treatment. The arrangement of each subject's pair of baseline and

post-final treatment photographs will be randomized such that the baseline photograph will be randomly assigned to the left or right side of the page. The order of subject photograph pairs will also be randomized. The reviewers will be blinded to the treatment parameters used, the subject data, the temporal order of photographs (before and after), and follow-up time point.

The reviewers will be asked to first determine the temporal order of each photograph pair, then rate the degree of improvement observed in the post-treatment photograph using the Physician's Global Assessment of Improvement Scale:

4 = Very Significant Improvement [REDACTED]

3 = Significant Improvement [REDACTED]

2 = Moderate Improvement [REDACTED]

1 = Mild Improvement [REDACTED]

0 = No Change [REDACTED]

4.3.1.2 [REDACTED]

4.3.2 [REDACTED]

[REDACTED] [REDACTED]

[REDACTED] [REDACTED]

[REDACTED]

[REDACTED]

4.3.3.2 [REDACTED]

[REDACTED]

[REDACTED]

[REDACTED]

[REDACTED]

4.4 [REDACTED]

[REDACTED]

[REDACTED]

[REDACTED]

[REDACTED]

[REDACTED]

[REDACTED]

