4.6 Photographs

Standardized digital photographs will be taken of each subject's face at baseline, prior to all laser treatments and at both follow-up visits. Any jewelry will be removed from the area being photographed. Hair will be pulled away from the face with a headband and subject will have recently cleansed skin. Facial photographs will be obtained from 3 angles: with the subject facing forward, 45° to the right and 45° to the left. Photographs will be taken in the same windowless room equipped with adequate lighting. The room lighting, camera positioning and subject positioning should be consistent for all study visit photographs. Digital camera settings should remain the same for all photographs and the highest resolution settings should be utilized.

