10.3.2 Analysis of Primary Endpoint

Formal statistical analysis is not planned for this study. The primary efficacy endpoint data, blinded reviewer degree of improvement at 12 weeks post-final treatment, will be summarized descriptively.

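### Does the blinded photograph reading need a written rule on locking answers and keeping a subject's two pairs apart?

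*Combined protocol and SAP*

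**What the plan says.** Section 4.3.1.1 of the combined protocol and SAP randomises twice. Within a pair, "the baseline photograph will be randomly assigned to the left or right side of the page". Across pairs, "The order of subject photograph pairs will also be randomized". The blinded reviewers (readers, below) do not know the treatment parameters, the subject data, or "the temporal order of photographs (before and after), and follow-up time point". They are "asked to first determine the temporal order of each photograph pair" and only then grade improvement from 0 (no change) to 4 (very significant).

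Section 4.6 has photographs taken "at baseline, prior to all laser treatments and at both follow-up visits" and standardises them: "The room lighting, camera positioning and subject positioning should be consistent for all study visit photographs".

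Section 4 describes an "open-label uncontrolled study in 15 male or female subjects"; section 5.1 says twenty subjects, so both numbers are carried below. For the primary endpoint, section 10.3.2 states: "Formal statistical analysis is not planned for this study".

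In section 4.3.1.1 one assessment time point and the text beside each scale grade are blacked out. Sections 4.3.1.2 and 6 are redacted.

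**The concern.** The study has no control arm and treatment is open, so the blinded reading is the main visible protection of the primary rating. A correct order call is informative only if it comes from a change the reader can see.

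Suppose a subject contributes two pairs, one per follow-up visit, and both use the same baseline picture. A reader who notices that one picture appears twice knows it is the baseline, and so knows the order of both pairs without judging the skin at all. Randomising sides does not prevent this, and randomising pair order does not guarantee that the two pairs are far apart. If the pairs are printed pages that stay open, the reader can lay them side by side. If answers are locked one by one, only the pair seen second is exposed, and only through memory. The readable text says neither which applies nor how a subject's pairs are separated.

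**Working it through.** The plan gives no power, alpha or sample-size figure to reproduce. The check has three parts.

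**1. Are there two pairs per subject?** Section 4.3.1.1 lists baseline, a redacted entry and 12 weeks; it blinds readers to the follow-up time point, which has little purpose with only one; and section 4.6 speaks of two follow-up visits. Against this, section 4.3.1.1 refers to each subject's pair in the singular. Two pairs is a reasonable inference, but it is not stated.

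**2. How far apart would a full shuffle put them?** With n subjects there are N = 2n pairs, and P(gap = k) = 2(N − k) / [N(N − 1)].

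- Back to back: 2/N = 2/30 = 0.067 for n = 15 and 2/40 = 0.050 for n = 20. Expected number of subjects: 15 × 2/30 = 1 and 20 × 2/40 = 1.
- At least one subject back to back, by inclusion-exclusion: 1 − Σ (−1)^k C(n,k) 2^k (2n − k)! / (2n)! = 0.638 for n = 15 and 0.637 for n = 20. A simulation for n = 15 gave 0.636.
- Within five positions: 270/870 = 0.310, or 4.7 of 15 subjects; 370/1560 = 0.237, or 4.7 of 20.

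So a shuffle alone does not ensure separation. These figures describe spacing only and do not measure harm.

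**3. What could recognition do to the order calls?** Assumptions: one reader sees both pairs, the same baseline picture is used in both, there is no visible effect, and the reader spots the repeat with probability r and otherwise guesses. The documents give no r, so a range is shown.

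- Pages open: P(correct at 12 weeks) = r + (1 − r) × 0.5 = 0.5 + 0.5r. Extra correct calls = n × 0.5r.
- Answers locked: the 12-week pair is seen second half the time, so P = 0.5 + 0.25r. Extra correct calls = n × 0.25r.

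| r | Open: correct | Extra of 15 / of 20 | Locked: correct | Extra of 15 / of 20 |
|---|---|---|---|---|
| 0.1 | 55% | 0.75 / 1 | 52.5% | 0.375 / 0.5 |
| 0.25 | 62.5% | 1.875 / 2.5 | 56.25% | 0.94 / 1.25 |
| 0.5 | 75% | 3.75 / 5 | 62.5% | 1.875 / 2.5 |
| 1 | 100% | 7.5 / 10 | 75% | 3.75 / 5 |

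For a given r, locking halves the excess over 50% and does not remove it. In practice r need not be the same with open and locked pages.

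The table stops at the order call, but the primary endpoint is the degree of improvement. The readable text does not say how a right or wrong call alters the score, so the table cannot be turned into a shift on the 0 to 4 scale. Where nothing has visibly changed, a reader who knows the order can still choose 0. Where the change is visible, the reader can often order the pair anyway, and recognition adds less.

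**The case for a change.** The strongest case for a change is that the safeguard is one the plan itself chose, and that a sentence on locking and separation would need no extra readers, pictures or ratings. The pictures are of faces, so a reader may well notice that two pairs show one person. The readable sentences on randomisation and blinding in section 4.3.1.1 run on without a gap, so a locking rule is unlikely to be hidden among them, although it could sit in a redacted section. Nor does a descriptive analysis repair a broken blind.

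The mechanism stands, and so does the value of locking as good practice. What does not stand is that the plan is wrong without it. No stated rule conflicts with another or gives a wrong result. The leak needs one reader for both pairs, an identical baseline image, recognition, and use of what was recognised; the documents state none of these. The word page does not establish that earlier pages stay open, and the uniform photography in section 4.6 makes recognition from memory harder.

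A written rule also has its own costs. Locking stops readers from going back to recalibrate earlier ratings. Splitting the reading into two halves with the same subject order fixes every gap at n, but then each repeat falls exactly n places later, so a reader who notices one can predict the rest; it also narrows the random pair order that the plan already has. With time points balanced between halves, the 12-week pair is still seen second, and so still exposed to memory, for 7 or 8 of 15 subjects (10 of 20).

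**Conclusion.** No change to the plan is needed. Section 4.3.1.1 already fixes what a protocol should fix: random sides, random pair order, blinding to temporal order and time point, and an order call before the rating. Whether answers are locked and how repeat pairs are spaced are details that whoever assembles the reading can settle sensibly in the reading instructions, and redacted text may already cover them.

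The possible excess in correct order calls runs from under one subject in 15 at r = 0.1 to 7.5 in 15 at the extreme of certain recognition with open pages. All of it rests on an assumed r, an inferred second pair, a shared baseline picture, one reader for both pairs and no visible effect. The consequence for the primary rating is not known, and that rating is summarised descriptively without a test or success threshold in the readable text, so no formal decision there turns on it. Confidence is moderate, because the second time point and the neighbouring sections cannot be read.

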5.1.2 Exclusion Criteria

Subjects will be excluded from the study if they meet any of the following Exclusion Criteria:

1.	Participation in a clinical trial of another device or drug within 6 months prior to enrollment or during the study.
2.	Any type of prior cosmetic treatment to the target area within 6 months of study participation, such as laser or light-based procedures or surgery.
3.	Prior injection to the face of botulinum toxin, collagen, hyaluronic acid filler or other dermal filler within 6 months of study participation, as applicable.
4.	Systemic use of retinoid, such as isotretinoin, or corticosteroid, as applicable, within 6 months of study participation.
5.	Use of topical medications on the face, such as antibiotics, benzoyl peroxide, retinoids (isotretinoin), corticosteroids, hydroquinone, or products containing dihydroxyacetone or alpha-hydroxy with concentration > 8%, within 1 month of participation.
6.	History of malignant tumors in the target area.
7.	Skin abnormalities in the target area, e.g., cuts, scrapes, wounds, scars, large moles.
8.	Pregnant and/or breastfeeding.
9.	Having an infection, dermatitis or a rash in the treatment area.
10.	Significant concurrent illness, such as diabetes mellitus or cardiovascular disease, e.g., uncontrolled hypertension.
11.	Suffering from coagulation disorders, or taking prescription anticoagulation medication which might make study participation unsafe according to Investigator's discretion.
12.	History of keloid scarring, hypertrophic scarring or of abnormal wound healing.
13.	History of immunosuppression/immune deficiency disorders or currently using immunosuppressive medications.
14.	History of vitiligo, eczema, or psoriasis.
15.	History of connective tissue disease, such as systemic lupus erythematosus or scleroderma.
16.	History of seizure disorders due to light.
17.	Any use of medication that is known to increase sensitivity to light according to Investigator's discretion.
18.	History of disease stimulated by heat, such as recurrent herpes simplex and/or herpes zoster (shingles) in the treatment area, unless treatment is conducted following a prophylactic regimen

19.	History of radiation to the treatment area or undergoing systemic chemotherapy for the treatment of cancer.
20.	History of pigmentary disorders, particularly tendency for hyper- or hypo-pigmentation.
21.	Anytime in life, having have used gold therapy (gold salts) for disorders such as rheumatologic disease or lupus.

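### The visible primary scale stops at no change, so a face that looks worse after treatment cannot be recorded as worse, and any mean grade can be raised

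*Combined protocol and SAP*

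**What the plan says.** The primary endpoint (section 4.1.1.1) is the degree of improvement 12 weeks after the last treatment, judged from photographs by independent blinded physicians, called readers below. Section 4.3.1.1 randomises left and right placement within each pair, and readers are masked to, among other things, "the temporal order of photographs (before and after), and follow-up time point". They first call the order, "then rate the degree of improvement observed in the post-treatment photograph using the Physician's Global Assessment of Improvement Scale".

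The scale starts at "4 = Very Significant Improvement" and descends through significant, moderate and mild improvement to level 0, labelled as no change. Heading 4.3.1.2 follows. Each label has redacted text after it, which looks like a descriptor of that level. No visible text says how to grade a later photograph that looks worse, or how to score a pair put in the wrong order.

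On analysis, section 10.3.2 says "Formal statistical analysis is not planned for this study" and that the "blinded reviewer degree of improvement at 12 weeks post-final treatment, will be summarized descriptively". It names no mean, median or proportion. Section 10.3.1 says that missing efficacy data are not imputed.

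**The concern.** Take a pair whose order the reader calls correctly. If the later photograph is better, or no different, the scale has a level for it. If it looks worse, no visible level fits. The nearest is 0, and a record of 0 then states that nothing changed.

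The study has no control arm, so the distribution of blinded grades is the whole primary result. If worsened faces are recorded as 0, a reader of the report cannot tell how many of the 0 grades were unchanged and how many were worse, and a mean grade comes out too high. The plan does treat adverse skin change as a possibility, since section 5.1.2 excludes people with "History of pigmentary disorders, particularly tendency for hyper- or hypo-pigmentation". That exclusion also lowers the expected frequency among those enrolled, so it shows that worsening is conceivable, not that it is common.

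**Working it through.** The plan gives no expected grade, sample-size calculation or power, so there is no figure of its own to reproduce.

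**Inputs.** Scale 0 to 4 (section 4.3.1.1). n = 15 (Protocol Summary and section 4); section 5.1 says twenty, so both are shown. The number k of worsened faces and the depth d in grades are assumptions, because the documents give neither. One grade per subject is assumed.

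**Step 1: effect of the floor on a mean.** If k of n faces are worse by d grades and are scored 0, the sum rises by k·d and the mean by k·d/n. With d = 1:

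| k | n = 15 | n = 20 |
|---|---|---|
| 0 | 0 | 0 |
| 1 | 1/15 = 0.07 | 1/20 = 0.05 |
| 2 | 2/15 = 0.13 | 2/20 = 0.10 |
| 3 | 3/15 = 0.20 | 3/20 = 0.15 |
| 5 | 5/15 = 0.33 | 5/20 = 0.25 |

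**Step 2: other summaries.** Moving a negative grade to 0 does not carry it past 1 or 2, so the proportions at 1 or above and at 2 or above stay as they are. With n = 15 the median is the 8th ordered value, so it changes only if 8 or more faces are worse.

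**Step 3: the ways a worsened face can enter the data.** Invented example with 15 subjects: 4 at +2, 5 at +1, 3 at 0, 2 at −1, 1 at −2. The non-negative grades sum to 8 + 5 = 13, and the signed sum is 13 − 4 = 9.

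| Handling of the 3 worsened faces | Mean | Grade ≥ 1 | Grade ≥ 2 | Median |
|---|---|---|---|---|
| Signed grade kept | 9/15 = 0.60 | 9/15 = 60% | 4/15 = 27% | 1 |
| Scored 0 | 13/15 = 0.87 | 9/15 = 60% | 4/15 = 27% | 1 |
| Left blank and dropped | 13/12 = 1.08 | 9/12 = 75% | 4/12 = 33% | 1 |
| Order reversed, rated improved by the same amount | 17/15 = 1.13 | 12/15 = 80% | 5/15 = 33% | 1 |

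In the second row, level 0 holds 6 of 15 subjects where 3 of 15 were unchanged. In the last row the sum is 13 + 1 + 1 + 2 = 17. The protection of the proportions in step 2 therefore holds only when the face is scored 0 and kept in the denominator.

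**Step 4: a model of the floor alone.** Assume that perceived change is normal, rounded to whole grades from −4 to 4, with every order call correct. The rise in the mean is the sum over j ≥ 1 of P(grade ≤ −j). For a true mean of 0 and SD 1 this is 0.309 + 0.067 + 0.006 + 0.000 = 0.38.

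| True mean | SD 0.5 | SD 0.75 | SD 1.0 |
|---|---|---|---|
| 0 | 0.16 | 0.28 | 0.38 |
| 0.5 | 0.02 | 0.10 | 0.18 |
| 1 | 0.00 | 0.02 | 0.07 |

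With a true mean of 0, 16%, 25% and 31% of faces look worse under these three SDs. These values illustrate the floor; they do not estimate its size in this study.

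**The case against.** The strongest objection is that the reading procedure leaves little room for the floor to act. A reader masked to order who finds one photograph worse will tend to call it the baseline. Worsening then mostly enters as a wrongly ordered pair rated as improved, and not as a correctly ordered pair held at 0. This stands. It makes the first row of the step 4 table an unlikely combination, because with no average change the order calls should be near chance and not all correct. The floor route is narrow but not empty: the assessment covers wrinkles, pigment, redness, vessels and texture together, so a reader may identify the order from one feature and still see net worsening.

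It also stands that scoring such a face 0 is an inference. No visible rule says so, and a reader might leave the item blank.

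Two further inferences are tempting. One is that reading noise can only push the summary up. It cannot be put that way: away from the floor a true 2 can be read as 1, and the cap at 4 pulls down. The other is that worsening will go wholly unreported. Section 7.2 requires observed adverse signs to be recorded whatever their severity, and section 10.3.4 counts subjects per event term. The table of contents also lists a second blinded assessment and several others whose text is redacted. The adverse-effect record is made at the site of an open-label study, so it does not replace a masked judgement of the photographs.

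Finally, an improvement-only scale is partly a design choice in a small descriptive study. That limits the severity, but it does not supply the missing count.

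**Conclusion.** The point holds in a limited form. As far as the text is visible, the primary scale has no place for a face that looks worse. If such faces are scored 0, the 0 row mixes two outcomes and a mean is raised by k·d/n: 0.07 for one face and 0.20 for three, with 15 subjects and one grade each. Proportions at 1 or above and 2 or above are then unaffected, and the median is unaffected unless more than half of the faces are worse.

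A reader might infer that the primary result is biased upward, by 0.16 to 0.38 grade. The documents do not support that. The plan names no mean, the shift is zero if no face is seen as worse, and that range assumes both no average change and perfect order calls. With a true mean of 1 grade the same model gives at most 0.07.

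The size in this study cannot be derived from the plan, and the missing rule for wrongly ordered pairs may matter more than the floor. The conclusion rests on the visible scale being complete; a rule hidden by redaction cannot be fully excluded. The gap does not invalidate a descriptive study, but it should be closed before the photographs are read.

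**What to change.** In section 4.3.1.1:

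- Add at least one level below zero (−1 = worse), or negative grades that mirror 1 to 4. The mirrored form is preferable if a mean will be reported. Alternatively, keep 0 to 4 and add a better/same/worse tick for each pair.
- Tell readers that the later photograph may be worse.
- State that, after unmasking, a wrongly ordered pair rated as improved receives the negative of its grade and never a positive grade. This rule and the new level belong together: without it, worsened faces would stay hidden and a nearly empty row for worse would reassure falsely.

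In section 10.3.2, report the number and percentage of subjects at every level, including worse, and compute any mean or median on the signed grade. If only the tick is used, show the number worse beside the primary table. The 0 to 4 distribution can still be shown by collapsing negative grades to 0.

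The cost is one or more added levels on the reader form, a scoring rule and extra table rows, with no new reader, visit or photograph. The downside is that the summary may be slightly less favourable and less directly comparable with studies that used 0 to 4. If the form is not changed first, worse ratings could be recovered only by reading the photographs again.
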